### 11.3 Other Response Criteria:

#### 11.31 Cutaneous Response Criteria:

Lesions will be measured by physical exam and photographed to evaluate for response. Photographs of the skin lesions, marked with a ruler, will be saved/uploaded in QREADS for comparison purposes.

If all target lesions are cutaneous, then the following modified Lugano criteria will be utilized. However, if at least one target lesion is not cutaneous, then the cutaneous measurements will be grouped with the target nodal/extranodal lesions when calculating the SPD and the response criteria per section 11.2 will be utilized with reference to the table below for cutaneous definitions whenever applicable.

Modified Lugano Criteria for Cutaneous Lesions	
Response	Definition
Complete response	100% clearance of all skin lesions
Partial response	$\geq 50\%$ decrease in SPD of up to 6 target measurable cutaneous lesions and not meeting Complete response definition
Stable disease	$< 50\%$ decrease from baseline in SPD of up to 6 target measurable cutaneous lesions; no criteria for progressive disease are met

Modified Lugano Criteria for Cutaneous Lesions	
Response	Definition
Progressive disease	
≥50% increase from nadir in SPD of up to 6 target measurable cutaneous lesions;
 
New cutaneous lesions

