#### 11.21 Complete Response (CR).

The designation of CR requires all of the following:

- 11.211 Complete disappearance of all detectable clinical evidence of disease and definitely disease-related symptoms if present before therapy.
- 11.212 All lymph nodes and nodal masses must have regressed on CT to normal size ( $\leq 1.5$  cm in their greatest transverse diameter for nodes  $> 1.5$  cm before therapy). Previously involved nodes that were 1.1 to 1.5 cm in their long axis and more than 1.0 cm in their short axis before treatment must have decreased to  $\leq 1.0$  cm in their short axis after treatment.
- 11.213 The spleen and/or liver, if considered enlarged before therapy on the basis of a physical examination or CT scan, should not be palpable on physical examination and should be considered normal size by imaging studies, and nodules related to lymphoma should disappear. However, determination of splenic involvement is not always reliable because a spleen considered normal in size may still contain lymphoma, whereas an enlarged spleen may reflect variations in anatomy, blood volume, the use of hematopoietic growth factors, or causes other than lymphoma. Similarly, other organs considered to be enlarged before therapy due to involvement by lymphoma, such as liver and kidneys, must have decreased in size.

11.214 If the bone marrow was involved by lymphoma before treatment, the infiltrate must have cleared on repeat bone marrow biopsy. The biopsy sample on which this determination is made must be adequate (with a goal of >20 mm unilateral core). If the sample is indeterminate by morphology, it should be negative by immunohistochemistry. A sample that is negative by immunohistochemistry but that demonstrates a small population of clonal lymphocytes by flow cytometry will be considered a CR until data become available demonstrating a clear difference in patient outcome.

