#### 11.22 Criteria for Partial Response (PR)

The designation of PR requires all of the following:

11.221 At least a 50% decrease in sum of the product of the diameters (SPD) of up to six of the largest dominant nodes or nodal masses. These nodes or masses should be selected according to all of the following:

- they should be clearly measurable in at least 2 perpendicular dimensions
- if possible they should be from disparate regions of the body
- they should include mediastinal and retroperitoneal areas of disease whenever these sites are involved

11.222 No increase should be observed in the size of other nodes, liver, or spleen.

11.223 Splenic and hepatic nodules must regress by  $\geq 50\%$  in their SPD or, for single nodules, in the greatest transverse diameter.

11.224 With the exception of splenic and hepatic nodules, involvement of other organs is usually assessable and no measurable disease should be present.

11.225 Bone marrow assessment is irrelevant for determination of a PR if the sample was positive before treatment. However, if positive, the cell type should be specified (eg, large-cell lymphoma or small neoplastic B cells). Patients who achieve a CR by the above criteria, but who have persistent morphologic bone marrow involvement will be considered partial responders.

When the bone marrow was involved before therapy and a clinical CR was achieved, but with no bone marrow assessment after treatment, patients should be considered partial responders.

11.226 No new sites of disease should be observed.

11.227 CT criteria should be used.

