#### 11.24 Relapsed Disease (after CR)/Progressive Disease (after PR, SD)

Lymph nodes should be considered abnormal if the long axis is more than 1.5 cm regardless of the short axis. If a lymph node has a long axis of 1.1 to 1.5 cm, it should only be considered abnormal if its short axis is more than 1.0. Lymph nodes  $\leq 1.0 \times \leq 1.0$  cm will not be considered as abnormal for relapse or progressive disease.

- 11.241 Appearance of any new lesion more than 1.5 cm in any axis during or at the end of therapy, even if other lesions are decreasing in size. Increased FDG uptake in a previously unaffected site should only be considered relapsed or progressive disease after confirmation with other modalities. In patients with no prior history of pulmonary lymphoma, new lung nodules identified by CT are mostly benign. Thus, a therapeutic decision should not be made solely on the basis of the PET without histologic confirmation.
- 11.242 At least a 50% increase from nadir in the SPD of any previously involved nodes, or in a single involved node, or the size of other lesions (eg, splenic or hepatic nodules). To be considered progressive disease, a lymph node with a diameter of the short axis of less than 1.0 cm must increase by 50% and to a size of 1.5 x 1.5 cm or more than 1.5 cm in the long axis.
- 11.243 At least a 50% increase in the longest diameter of any single previously identified node more than 1 cm in its short axis.
- 11.244 Transformation to a more aggressive histology that requires a change in active treatment will be considered progressive disease.

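### The response table for patients with only cutaneous targets (11.31) uses skin findings alone, so, read literally, non-cutaneous disease does not prevent a CR or PR that counts as a primary success

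*Combined protocol and SAP*

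**What the plan says.** Section 11.31 sets two branches.

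- All targets in the skin: "If all target lesions are cutaneous, then the following modified Lugano criteria will be utilized".
- At least one target elsewhere: skin measurements join the SPD and "the response criteria per section 11.2 will be utilized with reference to the table below for cutaneous definitions whenever applicable".

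In the all-cutaneous table, CR is "100% clearance of all skin lesions". PR is a fall of at least 50% in the SPD of up to six "target measurable cutaneous lesions and not meeting Complete response definition". PD is a rise of at least 50% in cutaneous SPD from nadir, or "New cutaneous lesions". No row mentions nodes, liver, spleen, marrow, non-target disease or a new site outside the skin.

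For other patients, 11.211 makes CR depend on "Complete disappearance of all detectable clinical evidence of disease". For PR, 11.222 allows no growth of other nodes, liver or spleen, and 11.226 adds "No new sites of disease should be observed". Under 11.241, PD includes "Appearance of any new lesion more than 1.5 cm in any axis during or at the end of therapy". Table 11.2 requires no new lesions for CR, PR and SD.

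Two general statements also bear on the point. The note that opens Section 11.0 uses the whole-body scan to assess target and non-target lesions. Section 16.41 bases overall response and time to progression on whole-body CT or PET/CT by the standard criteria, as set out in Section 11.

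Sections 16.11 and 16.3211 count any PR or CR as a success and do not treat cutaneous patients separately.

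**The concern.** Skin lesions need their own way of being measured, and 11.31 supplies one. The table goes further than that. It leaves out the conditions that stop a patient with lymphoma elsewhere from being called a responder. The sentence that brings 11.2 back is written as the alternative branch, so it does not restore those conditions for the all-cutaneous patient.

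The branch can be reached. T-cell lymphoma is eligible (3.14), and 3.15 asks for three measurable lesions without requiring any to be nodal.

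The primary endpoint is at stake. Section 1.7 states a hypothesis of anti-tumor immunity and regression of lymphoma, and 16.41 treats non-cryoablated lesions as the marker of systemic response. A success recorded despite new disease outside the skin would count against that purpose. Two assessors reading the same scan could also reach opposite primary outcomes, depending on which part of Section 11 they follow.

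**Working it through.** **1. The two sets of rules side by side.** Each case is a patient whose targets are all cutaneous.

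| Finding | 11.31 table, read literally | 11.2 and 11.21 to 11.24 |
|---|---|---|
| Skin cleared, new liver lesion over 1.5 cm | CR, success | PD (11.241, Table 11.2) |
| Skin SPD down at least 50%, new node over 1.5 cm | PR, success | PD (11.241); PR barred by 11.226 |
| Skin SPD down at least 50%, non-target nodes growing | PR, success | Not PR (11.222); PD if growth meets the PD rule |
| Skin cleared, marrow involved before and after | CR, success | PR (11.225), still a success |

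The last row limits the concern. Persisting marrow disease changes the CR rate but not the ORR. A success is lost through a new lesion, through non-target growth, or through organ disease that fails the PR conditions in 11.223, 11.224 or the spleen row of Table 11.2.

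**2. Who can be affected.** Table 11.2 takes up to six of the largest nodes, masses and extranodal lesions as targets, preferably from disparate regions. Section 11.221 adds mediastinal and retroperitoneal disease where involved. Measurable disease outside the skin would therefore usually supply a target and put the patient under 11.2. Three routes remain:

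- a new non-cutaneous lesion, which cannot change targets chosen at baseline;
- non-measured or marrow disease;
- lesions left out once six skin targets have been taken.

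The cryoablated lesion is excluded from response in every branch, so it plays no part.

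**3. The plan's own figures (16.31 to 16.314).** Inputs: N = 28, success at 13 or more, null ORR 30%, target ORR 53%, one-sided 0.05, power 81%.

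- Type I error = P(X ≥ 13), X ~ Bin(28, 0.30) = 0.0491.
- Power = P(X ≥ 13), X ~ Bin(28, 0.53) = 0.8122.

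Both agree with the plan. The margin below 0.05 is 0.05 − 0.0491 = 0.0009.

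**4. One false success.** 1/28 = 3.6 percentage points. 12/28 = 42.9% is ineffective and 13/28 = 46.4% is promising.

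**5. Sensitivity, on assumed inputs.** Let k of the 28 patients be all-cutaneous, and let f be the chance that a true non-responder among them is recorded as CR or PR. The documents give neither. Each such patient succeeds with probability 0.30 + 0.70f under the null, and the type I error is P(X1 + X2 ≥ 13), with X1 ~ Bin(28 − k, 0.30) and X2 ~ Bin(k, 0.30 + 0.70f).

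| k | f = 0.1 | f = 0.25 | f = 0.5 | f = 1 |
|---|---|---|---|---|
| 0 | 0.0491 | 0.0491 | 0.0491 | 0.0491 |
| 1 | 0.0522 | 0.0568 | 0.0645 | 0.0798 |
| 2 | 0.0554 | 0.0654 | 0.0835 | 0.1253 |
| 3 | 0.0588 | 0.0750 | 0.1067 | 0.1894 |

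Every computed entry with k of at least 1 exceeds 0.05, but that mainly reflects the 0.0009 margin. The high values need f of 0.5 or 1, meaning that half or all of the true non-responders in the branch are scored as responders.

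**The case against.** The best defence is that the table only replaces CT measurement for lesions followed by examination and photograph. Its title refers to cutaneous lesions. Nothing in 11.31 says that scans are disregarded or that 11.211, 11.226 and 11.241 cease to apply. The Section 11.0 note has no cutaneous exception, and 16.41 relies on whole-body imaging. On this view an assessor would never call a patient with a new liver lesion a responder. Target selection also returns most patients with measurable disease elsewhere to 11.2, and the documents do not show that any all-cutaneous patient was enrolled.

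Much of this stands. It rules out saying that the plan sets out to ignore systemic failure, and it makes the affected group narrow and possibly empty. It does not remove the conflict. Neither general statement says how a scan finding alters a category assigned under 11.31, and 16.41 points back to Section 11, which contains 11.31. Target selection does nothing about lesions that appear later. If assessors would in practice apply 11.2 anyway, the written rule should say so.

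A reader might also infer that PFS and duration of response are judged by the lenient rule. The documents do not establish this, because 16.41 ties time to progression to whole-body imaging and the standard criteria.

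**Conclusion.** The point holds as a conflict within the response rules. For all-cutaneous patients, the 11.31 table read literally lets a CR or PR stand despite new lesions outside the skin or failing non-target disease, and that result feeds the primary endpoint. The passages cited above point the other way without resolving it.

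The size is unknown. One false success is worth 3.6 points of ORR and matters most at 12 versus 13 of 28. For that to happen, one patient must have only skin targets, a skin response of at least 50%, disease elsewhere that would bar a response under 11.2, and an assessor who follows the table literally.

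A reader might infer that the type I error is inflated to somewhere between 0.052 and 0.107, the range for 1 to 3 patients and f from 0.1 to 0.5. The documents do not support that as an estimate: k and f are both assumed, and with no such patient the error stays at 0.0491. A reader might also infer that any patient with persisting nodal or visceral lymphoma can be scored CR. Target selection closes most of that route.

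The correction is worth making because it concerns who counts as a responder and costs little.

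**What to change.** Add to 11.31, in substance:

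- The table replaces only the measurement of target lesions.
- The Table 11.2 conditions on non-target disease, marrow and new lesions at any site continue to apply to CR, PR and SD.
- New or progressing non-cutaneous disease that meets Table 11.2 is PD.

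A cross-reference from the Section 11.0 note and 16.41 would make clear that they govern this branch too.

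If any patient has been scored under 11.31, apply the same rule to that patient from the CT or PET/CT already scheduled at baseline and at Cycles 4, 8, 12 and 18. No new procedure is needed. N = 28, the cut-off of 13, the exact type I error of 0.0491 and the power of 0.812 are unchanged. The cost is a few sentences of protocol text and, at most, re-scoring of whichever patients fall in the branch. The downside is that the reported ORR could be slightly lower.

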#### **11.4 Patient Reported Outcomes: Quality of Life**

- 11.41 Patients will complete quality of life assessments at times documented in Section 4. The assessments will allow the patients to evaluate themselves regarding quality of life, concerns and symptoms. Patient reported outcome results do not impact any treatment related decisions.
- 11.42 Patients will complete the Functional Assessment of Cancer Therapy – Lymphoma (FACT-Lym). This assessment consists of the FACT-General (FACT-G) and the 15-item Lymphoma specific subscale.

The Functional Assessment of Cancer Therapy – General (FACT-G) was developed to measure quality of life in cancer patients receiving therapy. It was initially validated using classical test theory (CTT) methodology in a heterogeneous sample of 545 patients with cancer, 8% of whom had either leukemia or lymphoma. The FACT-G is comprised of four subscales: physical well-being (PWB; 7-items, score range 0-28), social/family well-being (SWB; 7-items, score range 0-28), emotional well-being (EWB; 6-items, score range 0-24), and functional well-being (FWB; 7-items, score range 0-28). Users of the FACT-G are able to generate an overall score and four subscale scores with ranges and distributions that are sample-specific. All questions in the FACT-G use a 5-point rating scale (0 = Not at all; 1 = A little bit; 2 = Somewhat; 3 = Quite a bit; and 4 = Very much). Provided more than 50% of the items comprising a subscale are answered, a subscale score is computed as the prorated sum of the item responses for that subscale. Prorating, which replaces missing values with the mean of the completed items for that subscale, has been shown to be an acceptable method of imputing missing data in the FACT instruments when more than 50% of the items are answered. The FACT-G total score is computed as the sum of the four subscale scores, provided the overall item response is at least 80% (i.e., at least 22 of the 27 items were answered) and has a possible range of 0-108 points. Negatively worded items are reverse scored prior to summing so that higher subscale and total scores indicate better Quality of Life (Cella, Tulsky et al. 1993).

The FACT-Lym adds a lymphoma-specific subscale to the FACT-G. The content in the lymphoma subscale (e.g., “I have night sweats” and “I am bothered by itching”) is targeted towards patients on active treatment (Hlubocky, Webster et al. 2013).

## 12.0 Descriptive Factors

- 12.1 Number of prior treatment regimens (any): 0, 1, 2 >3.
- 12.2 Current disease status: Newly diagnosed vs. residual vs. relapsed vs. refractory.
- 12.3 Previous Auto SCT: Yes vs. no.
- 12.4 Ann Arbor stage: 1 vs. 2 vs. 3 vs. 4 (see Appendix VII).
- 12.5 International Prognostic Index (IPI) (Shipp, 1993): low risk (0 or 1 risk factors) vs. low intermediate risk (2 risk factors) vs. high intermediate risk (3 risk factors) vs. high risk (4 or 5 risk factors) (see Appendix VII).
- 12.6 Follicular Lymphoma International Prognostic Index (FLIPI) (Solal-Celigny, 2004): low risk (0 or 1 risk factor) vs. intermediate risk (2 risk factors) vs. high risk (3-5 risk factors) (see Appendix VII).
- 12.7 MCL International Prognostic Index (MIPI) (Hoster, 2008): 0-3 vs 4-5 vs 6-11 (see Appendix VII).

## 13.0 Treatment/Follow-up Decision at Evaluation of Patient

**Note: For additional information regarding follow-up decision, please refer to the patient treatment schematic (Patient Map), located with the CRFs and supplementary materials.**

- 13.1 Patients who go off protocol at any time to receive non-protocol alternate treatment will go to event monitoring (see Section 4.4).
- 13.2 Patients who are CR, PR, or SD not requiring non-protocol alternative treatment will continue on initial active treatment per protocol for 18 cycles (12 months).

Once treatment is completed patients may receive an additional year of optional pembrolizumab treatment (provided approval from PI and sponsor).

- If no pembrolizumab treatment will be given, patients will go to Treatment Observation (see Sections 4.5 and 13.2) if additional DC is available for retreatment or Observation (see Section 4.3) if no additional DC is available for retreatment.
- If pembrolizumab treatment will be given, patients will receive treatment for up to an additional 18 cycles (12 months) then proceed to
  - Treatment Observation (see Sections 4.5 and 13.2), if additional DC is available for retreatment.
  - Observation (see Section 4.3) if additional DC s not available for retreatment.

### 13.3 Treatment Observation

- 13.31 If the patient has achieved CR, PR, or SD in initial treatment or optional pembrolizumab cycles, not requiring non-protocol alternative treatment, the patient will be observed at the following time points: 8 weeks after the last dose of treatment and then every 3 months for 1 year; followed by monitoring every 4 months for a year, then every 6 months until 4 years post registration.

During Treatment Observation , the patient may be retreated at any time

following PD (see Section 13.8).

- 13.4 Patients who complete Treatment Observation without PD will have completed the study 4 years post registration.
- 13.5 Patients who develop PD during initial active treatment in the DC + Pembrolizumab cycles, will go to the event-monitoring phase(see Section 4.4).
- 13.6 Patients who develop PD during initial active treatment receiving only Pembrolizumab (cycles 6+ on dose level 1 or cycles 8+ on dose level -1) will go to observation (see Section 4.4) or retreatment per clinical judgment.
- 13.7 Patients who develop PD during the optional Pembrolizumab treatment will:
- Go to retreatment if DC is available
  - Go to observation (see Section 4.3) if DC unavailable or if the patient refuses further treatment or if the clinician determines retreatment isn't feasible.
- 13.8 Patients who develop PD during the observation phase with no DC available for retreatment, will go to event monitoring (see Section 4.4).
- 13.9a Patients who develop PD during the treatment observation phase who have DC available will:
- Go to retreatment (see Section 13.9d).
  - Complete treatment observation (see Section 4.5) if patient refuses further treatment or if clinician determines retreatment isn't feasible.
- 13.9b Patients who go off protocol treatment due to adverse events or DLT during initial treatment will go to observation (see Section 4.3). If PD occurs in observation, patients will go to event monitoring (see Section 4.4).
- 13.9c Patients who go off protocol treatment for reasons other than adverse events during initial treatment will go to the event-monitoring phase (see Section 4.4).
- 13.9d **Retreatment**
- Retreatment can be considered at any time when deemed clinically safe.
- DC created from the original leukopheresis must be available
  - Tumor lesion(s) must be amenable to cryoablation.
- 13.9e Patient who complete retreatment without PD will go to observation followed by event monitoring. Patients who complete retreatment having PD will go to event monitoring.
- 13.9f **Ineligible**
- A patient is deemed *ineligible* if after registration, it is determined that at the time of registration, the patient did not satisfy each and every eligibility criteria for study entry. The patient may continue treatment off-protocol at the discretion of the physician as long as there are no safety concerns, and the patient was properly registered. The patient will go directly to the event-monitoring phase of the study (or off study, if applicable).
- If the patient received treatment, all data up until the point of confirmation of ineligibility must be submitted. Event monitoring will be required per Section 4.4 of the protocol.
  - If the patient never received treatment, on-study material must be submitted and the patient will go off study.

13.9g Major violation

A patient is deemed a *major violation*, if protocol requirements regarding treatment in cycle 1 of the initial therapy are severely violated that evaluability for primary end point is questionable. All data up until the point of confirmation of a major violation must be submitted. The patient will go directly to the event-monitoring phase of the study. The patient may continue treatment off-protocol at the discretion of the physician as long as there are no safety concerns, and the patient was properly registered. Event monitoring will be required per Section 4.4 of the protocol.

13.9h Cancel

A patient is deemed a *cancel* if he/she is removed from the study for any reason before any study treatment is given. On-study material and the End of Active Treatment/Cancel Notification Form must be submitted. No further data submission is necessary.

